## 2.0 INTRODUCTION

### 2.1 Background

Activating the immune system has been demonstrated to produce durable efficacious responses in human cancers (Hodi, 2010). Targeted monoclonal antibodies (mAbs) that bind to tumor-associated antigens and recruit a patient's immune system to kill the tumor cells via antibody-dependent cellular cytotoxicity (ADCC) are mainstay treatments in oncology. Research on enhancing the immune system to enable functional and numerical capacity of the patient's immune system to synergize with the mAb are coming to focus more recently (Messaoudene, 2017). Because interleukin-15 (IL-15) was initially identified through its ability to mimic interleukin-2 (IL-2)-induced T cell proliferation, the biochemical and functional relation between these cytokines was quickly investigated. The results validated the concept that stimulating T cell and natural killer (NK) cell responses could yield effective and durable responses. IL-15 is a cytokine that has many overlapping functions with IL-2, including the ability to promote anti-tumor responses. IL-15 signaling has been shown in the clinic to stimulate an array of downstream pathways in immune cells leading to increased cellular growth, decreased apoptosis, and enhanced activation and migration of specific immune cells (Conlon, 2015). Endogenous IL-15 plays a crucial role in the development, function, and survival of NK cells, NK T cells, CD8+ T cells, and intestinal intraepithelial lymphocytes (Grabstein, 1994; Berard, 2003; Schluns, 2004).

IL-15 is constitutively expressed by a large number of cell types and tissues, including monocytes, macrophages, dendritic cells, keratinocytes, fibroblasts and nerve cells (Grabstein, 1994). The receptor for IL-15 consists of the  $\alpha$  subunit and a common  $\beta\gamma$  subunit that shares the IL-2 receptor responsible for signal transduction (Giri, 1995). In addition, IL-15 receptor alpha (IL-15R $\alpha$ ) is expressed on antigen-presenting dendritic cells, monocytes, macrophages and lymphocytes. IL-15 signaling also enhances the cytolytic activity of CD8+ T cells and induces long-lasting antigen-experienced CD8+CD44 $^{hi}$  memory T cells.

NKTR-255 is a novel immunotherapeutic anti-cancer drug candidate CCI [REDACTED]

[REDACTED] The PEG moiety of NKTR-255 serves to extend the effective half-life ( $t_{1/2}$ ) relative to unconjugated rhIL-15. As a result, NKTR-255 is expected to provide sustained IL-15 biological activity without the need for daily dosing. Unlike other engineered IL-15 agents (eg, ALT-803 [Han, 2011]), NKTR-255 binds to IL-15R $\alpha$  and IL-2/IL-15R  $\beta\gamma$  subunits and has the potential to maintain the full spectrum of IL-15 biology, including sustained pharmacodynamic (PD) effects of both NK cells and CD8+ memory T cells.

NKTR-255 is being evaluated in hematological malignancies as a salvage regimen in a Phase 1 dose escalation/expansion trial (NCT04136756), testing the safety and efficacy of NKTR-255.

## 2.1.1 Expansion of NKTR-255 Clinical Development Plan for the Treatment of Solid Tumors

Natural killer cells are innate lymphoid cells endowed with cytolytic activity and a capacity to secrete cytokines and chemokines. Several lines of evidence suggest that NK cells play an important role in anti-tumor immunity by directly lysing tumor cells or through participating in ADCC in conjunction with a tumor targeted monoclonal antibody. High levels of NK cell infiltration have been associated with a better prognosis for some tumors, including solid tumors. However, NK cells are often underappreciated in solid tumors, leading to speculation that these cells might only be involved in the control of hematological malignancies and tumor metastasis (Brittenden, 1996; Halama, 2011). Several studies have shown that the natural cytotoxicity of peripheral blood is significantly lower in patients with solid tumors than in healthy individuals (Brittenden, 1996). More recently, colorectal tumors have been shown to be almost devoid of NK cells, despite efficient T cell infiltration (Halama, 2011).

Squamous cell carcinoma (SCC) accounts for more than 90% of all head and neck cancers and is ranked the sixth most common cancer worldwide, with more than 650,000 new cases and 330,000 deaths reported in 2018 (Vigneswaran, 2014; Bray, 2018). In the United States (US), head and neck squamous cell carcinoma (HNSCC) accounts for 3% of malignancies, with approximately 53,000 Americans developing head and neck cancer annually and 10,800 dying from the disease (Siegel, 2019). The 2 broad approaches to treatment include primary surgery and upfront definitive radiation therapy, either alone or in combination with chemotherapy (Gilbert, 2009). Pembrolizumab has become the new standard first-line treatment either alone or in combination with chemotherapy for patients with metastatic or unresectable, recurrent HNSCC (Rischin, 2019; Keytruda US package insert, 2020). Successful outcomes with pembrolizumab have garnered interest in other immunotherapy modalities as treatment options for HNSCC. Head and neck squamous cell carcinoma is an immunosuppressive disease associated with low absolute lymphocyte count, altered NK cell function, and impairment of tumor-infiltrating T lymphocytes with an important impact on clinical outcome (Ferris, 2004; Kuss, 2004; Dasgupta, 2005). It is therefore of interest to promote NK cell infiltration of tumors and to develop immunotherapeutic approaches designed to harness NK cell functions in the tumor bed, including those that aim to reinforce conventional anti-tumor therapies to increase the chances of successful treatment (Habif, 2019).

Colorectal carcinoma (CRC) is the third most common cancer affecting both males and females in the US; approximately 70% of CRC cases arise in the colon (Siegel, 2019). Globally, CRC is the third leading cause of cancer and cancer-related deaths worldwide (Demb, 2019). The last 15 years have seen major advances in the treatment of metastatic colorectal carcinoma (mCRC). The median survival duration is now approaching 2 years, and 5-year survival rates as high as 15% are reported in some trials of patients treated with chemotherapy alone (Masi, 2011). Cetuximab has emerged as a core agent, along with 5-fluorouracil, irinotecan, oxaliplatin, and bevacizumab, for overall mCRC management and to prolong survival (Lenz, 2007). More recently, antibody to programmed cell death protein 1 (anti-PD-1) agent pembrolizumab received

accelerated approval for the treatment of mismatch repair (MMR)-deficient (dMMR) or microsatellite instability-high (MSI-H) colorectal cancer that has progressed following treatment with a fluoropyrimidine, oxaliplatin, and irinotecan. However, microsatellite instability (MSI) is present only in a small subset of CRC patients and has an even lower incidence in the metastatic setting (4%-5%) (Battaglin, 2018). While there is clear clinical evidence for a therapeutic role of immune checkpoint inhibitors such as pembrolizumab, the vast majority of patients with proficient MMR or microsatellite stable tumors do not benefit from immunotherapy (Ciardiello, 2019). Thus, many patients exhaust standard treatment options without deriving benefit and are subsequently transitioned to palliative care even though they still have good performance status.

CCI

CCI

CCI

CCI

CCI

2.2 NKTR-255

CCI

[figure not shown]
[figure not shown]
CCI

### **2.2.3 Clinical Experience with NKTR-255**

NKTR-255 is being evaluated in hematological malignancies as a salvage regimen in a Phase 1 dose escalation /expansion trial (Nektar Study 18-255-02; NCT04136756), testing the safety and tolerability of NKTR-255.

CCI

A large rectangular area of the page is completely blacked out, obscuring several paragraphs of text. The word 'CCI' is printed in red at the top left corner of this redacted area.A large rectangular area of the page is completely blacked out, obscuring several paragraphs of text.A large rectangular area of the page is completely blacked out, obscuring several paragraphs of text.

# CCI

## 2.2.6 Selection of NKTR-255 Recommended Phase 2 Dose (RP2D)

A composite of clinical information will be used to select the RP2D based on safety and tolerability, PK, PD, and optimal biological response. Additional patients may be enrolled to refine the RP2D and a minimum of 6 patients will be required to define the RP2D.

### 2.2.6.1 Safety Considerations for NKTR-255 and Cetuximab Combination

Cetuximab is a targeted monoclonal antibody to EGFR and has been part of the treatment backbone for metastatic CRC since its approval in 2004 and for HNSCC since approval in 2006. The safety of cetuximab as monotherapy has been well characterized and summarized by several multicenter clinical studies ([Fakih, 2010](#); [Erbitux US package insert, 2021](#)). In this study, the loading dose of cetuximab will be given as monotherapy.

Infusion-related reactions occurred within minutes of administration of cetuximab (median: 15 minutes, range: 2 to 140 minutes). The time from start of cetuximab to onset of IRR correlated inversely with the grade of the IRR, whereby the onset of the IRR occurred much earlier with Grade 4 IRR and later with lower grades of IRR (median to onset of Grades 4, 3, 2, and 1 IRR were 5, 13.5, 22, and 25 minutes, respectively,  $p = 0.04$ ). Pharmacologic prophylaxis with antihistamines IV 30 to 60 minutes prior to the first dose has been shown to be effective in reducing IRR incidence ([Touma, 2014](#)).

CCI

CCI

CCI

### **3.0 OBJECTIVES**

#### **3.1 Primary Objectives**

The primary objectives are:

Phase 1b (Dose Escalation):

- To evaluate the safety and tolerability, as well as define the MTD and/or RP2D, of NKTR-255 in combination with cetuximab in relapsed or refractory (R/R) HNSCC CRC

Phase 2 (Dose Expansion):

- To evaluate the safety and tolerability of NKTR-255 monotherapy and NKTR-255 in combination with cetuximab in R/R HNSCC, CRC, **CCI**
- To evaluate the efficacy of NKTR-255 in combination with cetuximab in R/R HNSCC or CRC by assessing the ORR by Response Evaluation Criteria In Solid Tumors version 1.1 (RECIST 1.1)

#### **3.2 Secondary Objectives**

The secondary objectives are:

- To evaluate the efficacy of NKTR-255 monotherapy in R/R **CCI** by assessing the ORR by RECIST 1.1
- To evaluate the efficacy of NKTR-255 in combination with cetuximab and NKTR-255 monotherapy by assessing progression-free survival (PFS) and overall survival (OS)

**CCI**

**CCI**

CCI

## 4.0 SELECTION OF STUDY POPULATION

### 4.1 Inclusion Criteria

#### 4.1.1 Inclusion Criteria for All Patients

Each patient must satisfy all of the following criteria to be enrolled in the study (for both dose escalation and dose expansion phases):

1. Patients must be at least 18 years of age at study entry, and of any gender, race, or ethnicity.
2. Patients must be capable of understanding and providing a written informed consent.
3. Women of childbearing potential (WCBP) must have a negative serum pregnancy test (minimum sensitivity 25 IU/L or equivalent units of human chorionic gonadotropin [HCG]) at Screening and a negative serum or urine pregnancy test within 24 hours prior to dosing. Women of childbearing potential and men who are sexually active with WCBP must commit to use contraception as described in [Appendix 7](#), for the duration of the study and for 1 month after the last dose of NKTR-255 and 2 months after the last dose of cetuximab.
4. Histologically confirmed diagnosis of a locally advanced (not amenable to curative therapy such as surgical resection or radiotherapy) or metastatic cancer of the following histologies: HNSCC, CRC, **CCI**
5. Patients who have previously received cetuximab or other EGFR-directed therapies are excluded from Phase 2 of the trial, unless cetuximab was given as part of a primary treatment approach, with no progressive disease for at least 4 months following the end of prior cetuximab treatment.
6. Life expectancy > 12 weeks as determined by the Investigator
7. Eastern Cooperative Oncology Group performance status 0 or 1 ([Appendix 5](#))
8. Measurable disease per RECIST 1.1
9. Patients must have demonstrated adequate organ function within 14 days before Cycle 1 Day 1 (C1D1):
  - a. Estimated glomerular filtration rate  $\geq 40$  mL/min/1.73 m^2 calculated using the Chronic Kidney Disease Epidemiology Collaboration (CKD-EPI) Creatinine Equation (see [Appendix 6](#))

#### 4.1.2 Inclusion Criteria for Specific Tumor Types

A patient may be entered into this study only if he/she meets all of the following additional criteria specific to that patient's tumor type:

- Head and Neck Squamous Cell Carcinoma

1. Patients must have histologically or cytologically confirmed advanced, recurrent, or metastatic HNSCC that could not be treated with curative intent. "Advanced" is defined as either locally advanced HNSCC not amenable to curative surgery or radiotherapy or with distant metastases.
2. Patients who have undergone treatment with anti-PD-1 or antibody to programmed death-ligand 1 (anti-PD-L1) (together termed "anti-PD-(L)1") must have had the last dose of antibody at least 4 weeks prior to receiving any study drug and evidence of tumor progression before they can be enrolled into this study.
3. Patients must have known status by pathology for HPV and Epstein-Barr virus (EBV) in HNSCC, either metastatic or recurrent disease.
4. Patients must have experienced progression (or toxicity precluding additional treatment) on any first- or second-line platinum-based chemotherapy and anti-PD-(L)1 antibody, unless they are ineligible for such treatment, **OR**,
5. Patients must be ineligible for platinum-based (either cisplatin or carboplatin) chemotherapy or chemoradiation due to decline in renal function and/or patient's intolerance.

- Colorectal Cancer
  1. Patients must have a histologically or cytologically confirmed diagnosis of advanced CRC; patients in Phase 2 must have confirmed *KRAS* (US) or *RAS* (ex-US) wild type EGFR-expressing advanced CRC. "Advanced" is defined as either locally advanced unresectable cancer or metastatic disease.
  2. Patients must have received at least 2 prior cancer therapy regimens administered for metastatic disease including fluoropyrimidine, irinotecan, and oxaliplatin, unless ineligible or intolerant for such treatment.
  3. Patients with MSI-H or dMMR tumors must have been exposed to checkpoint inhibitors such as anti-PD-1.

A large, bold, red logo consisting of the letters "CCI" in a sans-serif font. The letters are outlined in red and filled with a lighter red color. They are positioned against a solid black rectangular background.

# CCI

## 4.2 Exclusion Criteria

Patients who meet any of the following criteria are ineligible:

1. Use of an investigational agent or an investigational device within 28 days before administration of first dose of study drug(s)
2. Patients who have an active, known, or suspected autoimmune disease. Patients requiring systemic treatment within the past 3 months or a documented history of clinically severe autoimmune disease that requires systemic corticosteroids or immunosuppressive agents (exceptions include any patient on 10 mg or less of prednisone or equivalent, patients with vitiligo, hypothyroidism stable on hormone replacement, Type I diabetes, chronic graft-versus-host disease, Graves' disease, Hashimoto's disease, alopecia areata, eczema, psoriasis, or with Medical Monitor approval).
3. History of allergy or known hypersensitivity to murine protein or study drug components
4. History of organ transplant that requires ongoing use of immunosuppressive agents
5. Patients who have been previously treated with IL-2 or IL-15

6. Patients with HNSCC who require treatment with anticoagulation therapy are not eligible. Use of warfarin for CRC, **CCI** [REDACTED] patients within 14 days of initiating study drug(s) is not permitted. Additional information about anti-coagulant therapy on treatment can be found in Section [5.10.3](#).
7. Known Grade 3 or 4 hypersensitivity reaction to cetuximab, history of allergy to red meat or tick bites, or history of positive test results for immunoglobulin E antibodies against cetuximab
8. Patient has had prior Grade 4 IRR to cetuximab
9. Unresolved toxicity from previous anti-cancer therapy, unless resolved to Grade  $\leq 1$  or baseline; or resolved to Grade 2 (with the exceptions outlined in the inclusion criteria or deemed clinically not significant, and approved by the Sponsor); or resulting from incomplete recovery from recent surgery (major)
10. Prior surgery or radiotherapy within 14 days of initiating study drug(s). Patients must have recovered from all acute radiation-related toxicities, not require corticosteroids, and have not had radiation pneumonitis.
11. Patients participating in observational studies should be discussed with the Medical Monitor to confirm eligibility.
12. Patients who have had  $< 28$  days since the last anti-cancer treatment, chemotherapy, or biological therapy, or  $< 14$  days from approved tyrosine kinase inhibitor therapy (sunitinib, sorafenib, vemurafenib, dabrafenib, cobimetinib), or systemic or inhaled steroid therapy at doses greater than 10 mg of prednisone or equivalent before administration of the first dose of study drug(s)
13. Patients who have received systemic interferon alpha (IFN $\alpha$ ) within the previous 6 months prior to enrollment in the study are not eligible.
14. Active infection requiring systemic therapy within 7 days prior to dosing
15. Evidence of clinically significant interstitial lung disease or active, noninfectious pneumonitis
16. Known immunodeficiency or active HIV (antibodies to HIV-1 or HIV-2). However, HIV-associated ASCC patients on effective anti-retroviral therapy with CD4+ count  $\geq 300/\mu\text{L}$  and undetectable viral load are eligible.
17. Known to be seropositive or active for hepatitis B or hepatitis C as defined in Section [5.13.6](#). Patients who had hepatitis B but have received an antiviral treatment and show non-detectable viral DNA for 3 months are eligible. Patients who are seropositive because of hepatitis B virus vaccine are eligible.
18. Prolonged Fridericia's corrected QT interval (QTcF)  $> 450$  ms for men and  $> 470$  ms for women at Screening
19. History of unstable or deteriorating cardiac disease within the previous 6 months prior to Screening including but not limited to the following:

- a. Unstable angina or myocardial infarction
- b. Congestive heart failure (New York Heart Association Class III or IV)
- c. Uncontrolled clinically significant arrhythmias

20. Has a known additional malignancy that is progressing or requires active treatment; exceptions include basal cell carcinoma of the skin, SCC of the skin that has undergone potentially curative therapy, or in situ cervical cancer. An incidental finding of prostate cancer (identified upon resection of the prostate) is acceptable, provided that the following criteria are met: Stage T2N0M0 or lower; Gleason score  $\leq 6$ , and prostate specific antigen below lower limit of normal by local laboratory.

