**CCI**

21. Patient has any of the following laboratory test results during Screening:

- a. Aspartate aminotransferase or ALT level  $\geq 2.5 \times$  the upper limit of normal (ULN)
- b. Alkaline phosphatase level  $\geq 2.5 \times$  ULN
- c. Total bilirubin level  $\geq 2 \times$  ULN (except for Gilbert Syndrome: direct bilirubin  $\geq 2 \times$  ULN)
- d. Potassium level  $< 3.0$  mEq/L; or  $> 10$  mEq/L
- e. Corrected serum calcium  $> 14.0$  mg/dL (3.5 mmol/L)
- f. Magnesium level  $< 1.0$  mg/dL

22. Patient is a woman who is pregnant or breastfeeding or planning to become pregnant while enrolled in this study or within 1 month after the last dose of NKTR-255 or within 2 months after the last dose of cetuximab.

23. Active brain metastases or leptomeningeal metastases patients with brain metastases are eligible if these have been treated and there is no radiographic evidence of progression for at least 4 weeks after treatment is complete (confirmed by the head imaging obtained within 28 days prior to study treatment). There must also be no requirement for immunosuppressive doses of systemic corticosteroids ( $> 10$  mg/day prednisone equivalents) for at least 4 weeks prior to study treatment. Stable dose of anticonvulsants is required within 14 days prior to study treatment. Treatment for central nervous system metastases may include stereotactic radiosurgery (eg, GammaKnife, CyberKnife, or equivalent) or neurosurgical resection. Patients who received whole brain radiation therapy are not eligible.

24. History of unstable hypertension and/or Screening blood pressure  $> 150/90$  millimeters of mercury (mmHg) (systolic/diastolic) with or without end organ damage; Screening blood pressure must be  $< 150$  mmHg for systolic blood pressure and  $< 90$  mmHg for diastolic blood pressure (by at least 1 and up to 3 observations taken during the Screening period).
25. Live, attenuated vaccines are prohibited within 30 days before the first dose of study drug (exception is made for vaccines against severe acute respiratory syndrome coronavirus 2 [SARS-CoV-2]; coronavirus disease 2019 [COVID-19]). For details, refer to Section 5.10.3.
26. Known current drug, alcohol, or tobacco abuse
27. Any condition including medical, emotional, psychiatric, or logistical that, in the opinion of the Investigator, would preclude the patient from adhering to the protocol

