#### 5.3.2 Cetuximab Dosing

In Phase 2 (Dose Expansion), cetuximab will only be administered in Cohorts A, B, C1, D1, and E1, and in patients in the monotherapy cohorts (Cohorts C, D, E, A1, and B1) who, after at least 1 tumor assessment, do not experience PR or CR per RECIST 1.1. In these patient groups, cetuximab 400 mg/m^2 IV will be given alone as a loading dose 7 days before the start of Cycle 1 (Day -7). Starting C1D1, cetuximab 250 mg/m^2 IV will be administered once weekly. **CCI**

Body surface area used in calculating cetuximab dose should be the same as the Day -7 value, unless there is a  $\geq 10\%$  change in weight or height of the patient in which case the body surface area will be re-calculated based on the new weight and height of that patient within a cycle.

For current information about administration and dose modification of cetuximab refer to the current local prescribing information, published on the local applicable website (eg, <http://base donnees-publique.medicaments.gouv.fr>).

The cetuximab dose may be reduced or adjusted based on review of available safety and tolerability data. Dose adjustment or discontinuation for cetuximab may be required based on emerging toxicities and should follow the guidelines specified in this protocol and in the current local prescribing information for cetuximab.

For Grade 1 or 2 IRRs, the infusion rate may be reduced by 50%. For Grade 3 or 4 IRRs, cetuximab must be immediately and permanently discontinued.

For additional information about cetuximab administration, refer to the current local prescribing information.

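### Exclusion 8 bars a prior Grade 4 infusion-related reaction to cetuximab but not a resolved Grade 3 one, although Section 5.3.2 ends cetuximab permanently at Grade 3

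*Protocol*

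**What the plan says.** **At entry.** Four items in Protocol Section 4.2 bear on an earlier reaction to cetuximab, and a fifth is a general backstop:

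- Exclusion 8: "Patient has had prior Grade 4 IRR to cetuximab".
- Exclusion 7: "Known Grade 3 or 4 hypersensitivity reaction to cetuximab", together with red-meat or tick-bite allergy and a positive test for IgE against cetuximab.
- Exclusion 3: "History of allergy or known hypersensitivity to murine protein or study drug components".
- Exclusion 9: "Unresolved toxicity from previous anti-cancer therapy", with allowances for toxicity that has resolved.
- Exclusion 27: a condition that, in the Investigator's opinion, "would preclude the patient from adhering to the protocol".

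Inclusion 5 in Section 4.1.1 limits earlier exposure, but only in one phase: "Patients who have previously received cetuximab or other EGFR-directed therapies are excluded from Phase 2 of the trial". It exempts patients whose earlier cetuximab belonged to their primary treatment and whose disease did not progress for at least 4 months afterwards.

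**On study.** Section 5.3.2 states: "For Grade 3 or 4 IRRs, cetuximab must be immediately and permanently discontinued". Section 5.7 includes a Grade 3 or 4 IRR in its list of events that end all assigned study drugs. It lets NKTR-255 continue, with Medical Monitor approval, when the toxicity is attributed to cetuximab alone.

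**Exposure.** In Phase 1b, Section 5.1.1 gives every patient 400 mg/m² of cetuximab at Day -7. Under Section 5.10.2, premedication for cetuximab is left to the Investigator.

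**The concern.** The protocol treats a Grade 3 IRR during the study as reason enough never to give that patient cetuximab again. Its entry rule for the same kind of reaction to the same drug starts one grade higher. A patient whose Grade 3 reaction occurred before enrolment can therefore be re-exposed, while a patient whose reaction occurred on study cannot.

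What is at stake is patient safety. If a Grade 3 or 4 IRR did recur, Section 5.3.2 would stop cetuximab, and Section 5.7 would stop all study drugs unless the Medical Monitor agreed to continue NKTR-255. If that happened at the loading dose, the patient would have taken the risk of re-exposure before receiving any NKTR-255.

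**Working it through.** No arithmetic applies. The check sets the grade limits side by side and then takes the patient in question through each visible criterion.

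| Rule | Event covered | Grade at which it acts |
|---|---|---|
| Exclusion 8 (4.2) | Prior IRR to cetuximab | 4 |
| Exclusion 7 (4.2) | Prior hypersensitivity to cetuximab | 3 or 4 |
| Section 5.3.2 | IRR on study: cetuximab stops | 3 or 4 |
| Section 5.7 | IRR on study (line does not name cetuximab): all study drugs stop, subject to the NKTR-255 exception | 3 or 4 |

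The entry limit for an IRR is one grade looser than the other three.

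Now take a patient who had cetuximab earlier and a Grade 3 reaction that was recorded as an IRR and has fully resolved.

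1. **Exclusion 8** does not apply, because the event was not Grade 4.
2. **Exclusion 7** applies only if the event is classed as hypersensitivity. The protocol lists IRR as a separate item with its own grade, so a site may well treat the two as distinct. If exclusion 7 already covered every IRR of Grade 3 or 4, exclusion 8 would be redundant.
3. **Exclusion 3** needs an allergy or hypersensitivity label and does not mention IRR.
4. **Exclusion 9** concerns unresolved toxicity, and this event has resolved.
5. **Exclusion 27** could be used, but it is discretionary, turns on adherence and sets no IRR grade.
6. **Inclusion 5** does not restrict earlier cetuximab in Phase 1b.

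The patient is therefore not explicitly excluded from Phase 1b and would meet cetuximab again at Day -7.

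In Phase 2 the route is narrower. The patient must first qualify for the exemption in inclusion 5, including the 4 months without progression. Under Section 5.3.2, cetuximab then goes only to Cohorts A, B, C1, D1 and E1, and to patients in the monotherapy cohorts without a partial or complete response after at least one tumor assessment. Section 5.3.1.4 makes that add-on optional and places its loading dose 7 days before the next scheduled NKTR-255 cycle. A monotherapy patient gets no cetuximab at entry and may never get any.

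The size of the affected group cannot be worked out. The documents give no rate of earlier cetuximab use, of earlier Grade 3 IRR, or of recurrence after one.

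**The case against.** The strongest reply is that the two rules do different jobs. Exclusion 8 concerns a past event, and Sections 5.3.2 and 5.7 concern an acute one. Both can be followed at once, and nothing visible requires the limits to match. Exclusions 7 and 8 also sit next to each other, which fits a deliberate two-tier rule: allergic-type reactions barred from Grade 3, other infusion reactions from Grade 4. This has some force. The difference is not a logical contradiction, and a two-tier intent is possible. But no visible text states that intent. Nor does it explain why a reaction that rules out further cetuximab on study should allow a fresh loading dose at entry.

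Other mitigating points stand. The group is narrow and depends on how the earlier event was labelled. Section 2.2.6.1 describes antihistamine prophylaxis as effective in reducing IRR incidence, and Section 7.14 requires access to intensive care. These lower the risk but do not set an entry limit. For cetuximab administration and dose modification the protocol defers to local prescribing information, which may limit re-treatment. That text is not available here, and the deferral does not amend Section 4.2.

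A reader might infer three stronger claims that the documents do not support:

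- *That the sponsor gave no rationale or classification rule.* Parts of Sections 2.2.6.1 and 7.3 and all of Section 5.11 are redacted, so this cannot be said.
- *That every exempted Phase 2 patient is re-exposed at Day -7.* The monotherapy cohorts show otherwise.
- *That a recurrence always ends all study treatment, or that recurrence is likely.* Section 5.7 allows NKTR-255 to continue in the stated case, and no recurrence rate is given.

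**Conclusion.** The point holds as a minor patient-safety gap in eligibility. In the visible text, a prior and resolved Grade 3 event recorded as an IRR is not explicitly excluded, although the same grade on study ends cetuximab permanently. The gap is one grade wide. It applies to Phase 1b and, in Phase 2, only to exempted patients who go on to receive cetuximab.

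The conclusion rests on two assumptions: that sites record some Grade 3 reactions as IRRs and not as hypersensitivity, and that no redacted text supplies a further bar. Confidence is medium for these reasons.

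No endpoint, estimate or planned analysis depends on this limit. SAP Sections 2.0 and 5.0 say that only Phase 1b patients were enrolled and that no Phase 2 patients were, so a change would matter only for further enrolment. It is a cheap improvement, not a flaw in the design or analysis.

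**What to change.** In Protocol Section 4.2, change the limit in exclusion 8 from Grade 4 to Grade 3 or 4 for a prior IRR to cetuximab. That brings it into line with Sections 5.3.2 and 5.7 and with the grade limit in exclusion 7. The visible synopsis criteria do not repeat exclusion 8, and the SAP needs no change.

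The cost is one grade limit in one sentence, plus a few previously treated candidates who become ineligible. Section 5.3.2 would have barred those same patients from further cetuximab had the reaction occurred on study. If Grade 4 was a deliberate choice, the alternative is to say so in the protocol and set safeguards for re-exposure after a Grade 3 IRR.
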